Change from Baseline to Weeks 104 and 208 in CSF biomarkers (i.e., CSF Weeks 104 and 208 only), including CXCL13, BAFF (B cell activating factor), TNF, IL-6, IL-10, IL-17, interferon-gamma, IL-4, IL-23, IL-8, soluble CD27 (sCD27), genetic risk factors (HLA-DRB1*15:01) or other emerging exploratory markers of disease biology as appropriate

Change from Baseline to Weeks 48, 104, and 208 in slowly evolving lesions (SEL)

Change from Baseline to Weeks 24, 48, 72, 104, 130, 156, 182 and 208 in peripheral blood immune cell population frequency and phenotype, including B cells, T cells and innate immune cells (monocyte, macrophage, neutrophils, natural killer cells, etc.)

Change from Baseline to Weeks 24, 48, 72, 104, 130, 156, 182 and 208 in peripheral blood biomarkers, including CXCL13, BAFF (B cell activating factor), TNF, IL-6, IL-10, IL-17, interferon-gamma, IL-4, IL-23, IL-8, soluble CD27 (sCD27), genetic risk factors (e.g., HLA-DRB1*15:01) or other emerging exploratory markers of disease biology as appropriate

Change from Baseline to Weeks 24, 48, 72, 104, 130, 156, 182 and 208 in patient reported outcomes, including quality of life, fatigue, depression, and disability, as measured by Neuro-QoL™

Change from Baseline to Weeks 24, 48, 72, 104, 130, 156, 182 and 208 in cognitive function and information processing speed as measured by symbol digit modality test (SDMT)

Correlation between changes in compartment-specific biomarkers of disease biology with radiologic and/or clinical disease outcomes

Correlation between changes in patient reported outcomes, including SDMT, and radiologic and/or clinical disease outcomes

Correlation between changes in compartment-specific immune cell subsets with radiologic and/or clinical disease outcomes.

Correlation between changes in NfL levels and radiologic and/or clinical disease outcomes

Correlation between changes in CSF abnormalities (OCB and IgG index) and radiologic and/or clinical disease outcomes

SAFETY OBJECTIVES

The safety objectives for this study are to evaluate the safety of ocrelizumab compared with placebo on the basis of the following endpoints:

Nature, frequency, severity, and timing of adverse events

Vital signs, physical findings, and clinical laboratory results during and following study drug administration

Adverse events related to biomarker sample collection

STUDY DESIGN

DESCRIPTION OF THE STUDY

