The above examples of dose interruption and slowing (for mild/moderate and severe IRRs) will result in a change in the infusion rate and increase the total duration of the infusion but not the total dose.

SAFETY PARAMETERS AND DEFINITIONS

Safety assessments will consist of monitoring and reporting adverse events (AEs) and serious adverse events (SAEs) per protocol. This includes all events of death and any study-specific issue of concern.

Adverse Events

An AE is any unfavorable and unintended sign (including an abnormal laboratory finding), symptom, or disease temporally associated with the use of an investigational medicinal product (IMP) or other protocol-imposed intervention, regardless of attribution.

This includes the following:

AEs not previously observed in the subject that emerge during the protocol-specified AE reporting period, including signs or symptoms associated with multiple sclerosis that were not present prior to the AE reporting period.

Complications that occur as a result of protocol-mandated interventions (e.g., invasive procedures such as cardiac catheterizations).

If applicable, AEs that occur prior to assignment of study treatment associated with medication washout, no treatment run-in, or other protocol-mandated intervention.

Preexisting medical conditions (other than the condition being studied) judged by the investigator to have worsened in severity or frequency or changed in character during the protocol-specified AE reporting period.

Serious Adverse Events

An AE should be classified as an SAE if the following criteria are met:

It results in death (i.e., the AE actually causes or leads to death).

It is life threatening (i.e., the AE, in the view of the investigator, places the subject at immediate risk of death. It does not include an AE that, had it occurred in a more severe form, might have caused death.).

It requires or prolongs inpatient hospitalization.

It results in persistent or significant disability/incapacity (i.e., the AE results in substantial disruption of the subject's ability to conduct normal life functions).

It results in a congenital anomaly/birth defect in a neonate/infant born to a mother exposed to the IMP.

It is considered a significant medical event by the investigator based on medical judgment (e.g., may jeopardize the subject or may require medical/surgical intervention to prevent one of the outcomes listed above).

Adverse Events of Special Interest

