AESIs are a subset of Events to Monitor (EtMs) of scientific and medical concern specific to the product, for which ongoing monitoring and rapid communication by the Investigator to the Sponsor is required. Such an event might require further investigation in order to characterize and understand it. Depending on the nature of the event, rapid communication by the trial Sponsor to other parties (e.g., Regulatory Authorities) may also be warranted.

Adverse events of special interest for this study include the following:

Cases of potential drug-induced liver injury that include an elevated ALT or AST in combination with either an elevated bilirubin or clinical jaundice, as defined by Hy's law:

Treatment-emergent ALT or AST $> 3 \times$ ULN in combination with total bilirubin $> 2 \times$ ULN

Treatment-emergent ALT or AST $> 3 \times$ ULN in combination with clinical jaundice

Data related to a suspected transmission of an infectious agent by the study drug (STIAMP), as defined below:

Any organism, virus, or infectious particle (e.g., prion protein transmitting transmissible spongiform encephalopathy), pathogenic or non-pathogenic, is considered an infectious agent. A transmission of an infectious agent may be suspected from clinical symptoms or laboratory findings that indicate an infection in a patient exposed to a medicinal product. This term applies only when a contamination of the study drug is suspected

There are no Ocrelizumab Events of Special Interest.

METHODS AND TIMING FOR ASSESSING AND RECORDING SAFETY VARIABLES

The investigator is responsible for ensuring that all AEs and SAEs that are observed or reported during the study, are collected and reported to the FDA, appropriate IRB(s), and Genentech, Inc. in accordance with CFR 312.32 (IND Safety Reports).

Adverse Event Reporting Period

The study period during which AEs and SAEs as described in Section 5.2 where the patient has been exposed to Genentech product must be reported. Reporting period begins after informed consent is obtained and initiation of study treatment and ends 24 weeks following the last administration of study treatment or study discontinuation/termination, whichever is earlier. After this period, investigators should only report SAEs that are attributed to prior study treatment.

Assessment of Adverse Events

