If known at the time of reporting, a diagnosis should be reported rather than individual signs and symptoms (e.g., record only liver failure or hepatitis rather than jaundice, asterixis, and elevated transaminases). However, if a constellation of signs and/or symptoms cannot be medically characterized as a single diagnosis or syndrome at the time of reporting, it is acceptable to report the information that is currently available. If a diagnosis is subsequently established, it should be reported as follow-up information.

Deaths

All deaths that occur during the protocol-specified AE reporting period (see Section 5.3.1), regardless of attribution, will be reported to the appropriate parties. When recording a death, the event or condition that caused or contributed to the fatal outcome should be reported as the single medical concept. If the cause of death is unknown and cannot be ascertained at the time of reporting, report "Unexplained Death".

Preexisting Medical Conditions

A preexisting medical condition is one that is present at the start of the study. Such conditions should be reported as medical and surgical history. A preexisting medical condition should be re-assessed throughout the trial and reported as an AE or SAE only if the frequency, severity, or character of the condition worsens during the study. When reporting such events, it is important to convey the concept that the preexisting condition has changed by including applicable descriptors (e.g., "more frequent headaches").

Hospitalizations for Medical or Surgical Procedures

Any AE that results in hospitalization or prolonged hospitalization should be documented and reported as an SAE. If a subject is hospitalized to undergo a medical or surgical procedure as a result of an AE, the event responsible for the procedure, not the procedure itself, should be reported as the SAE. For example, if a subject is hospitalized to undergo coronary bypass surgery, record the heart condition that necessitated the bypass as the SAE.

Hospitalizations for the following reasons do not require reporting:

Hospitalization or prolonged hospitalization for diagnostic or elective surgical procedures for preexisting conditions

Hospitalization or prolonged hospitalization required to allow efficacy measurement for the study or

Hospitalization or prolonged hospitalization for scheduled therapy of the target disease of the study

Assessment of Severity of Adverse Events

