The primary efficacy endpoint for this study is to evaluate the efficacy of ocrelizumab compared with placebo on delaying the time to development of new radiological or clinical evidence of MS, defined as the time from baseline to first new T1 gadolinium-enhancing lesions and/or new or enlarging T2 lesions consistent with MS OR first clinical evidence of MS, i.e., neurological event resulting from CNS demyelination as evidenced by acute or progressive clinical syndrome consistent with MS.

The time to development of radiological or clinical evidence of MS in the ocrelizumab arm and placebo arm will be compared and tested using a stratified log-rank test with the null and alternative hypotheses as follows:

H_0 : There is no difference in the time to onset of radiological or clinical evidence of MS between the ocrelizumab and placebo groups.

H_1 : There is a difference in the time to onset of radiological or clinical evidence of MS between the ocrelizumab and placebo groups.

The proportion of patients with radiological or clinical evidence of MS over time will be estimated using Kaplan-Meier methodology and the overall hazard ratio will be estimated using a stratified Cox proportional hazards model. In the presence of a large amount of interval censoring, stratified generalized log rank test and stratified proportional hazards model with full likelihood function will be used to compare survival between groups.

Estimands for the Primary Analysis

The primary analysis has a treatment-policy estimand (see ICH E9[R1] 2019) on the basis of the following attributes:

Population: All randomized patients.

Variable: Time from baseline to development of new radiological or clinical evidence of MS.

Intercurrent events:

Withdrawal from treatment: Patients will be followed until the primary analysis regardless of adherence to study treatment or reason for treatment withdrawal. Data will continue to be collected from such patients and included in the analysis, following a treatment-policy strategy.

Initiation of another MS therapy: Data will continue to be collected from such patients and included in the analysis, following a treatment-policy strategy.

Patients still ongoing and without an initial evidence of MS event at the time of study unblinding will be censored at the date of the last assessment.

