All verbatim adverse event terms will be mapped to MedDRA thesaurus terms, and adverse event severity will be graded according to CTCAE v5.0 grade. All adverse events, serious adverse events, adverse events leading to death, adverse events of special interest, and adverse events leading to study treatment discontinuation that occur on or after the first dose of study treatment (i.e., treatment-emergent adverse events) will be summarized by mapped term, appropriate thesaurus level, and severity grade. For events of varying severity, the highest grade will be used in the summaries. Deaths and cause of death will be summarized.

Associated laboratory parameters, such as hepatic function, renal function, and hematology values, will be grouped and presented together. Marked abnormalities will also be flagged.

BIOMARKER ANALYSES

Biomarkers will be assessed at baseline (screening) and subsequent time points following administration of ocrelizumab or placebo. Biomarkers levels at baseline or over time may be compared with efficacy or safety measurements to assess prognostic or

predictive properties. Biomarkers may also be analyzed over time as absolute values and/or percent change relative to baseline over time, and may be compared with efficacy, other biomarkers, or safety measurements.

INTERIM ANALYSES

The iDMC will review interim analyses as specified in the iDMC Charter. Interim analyses will be conducted by the unblinded statistician(s) and will focus on recruitment/enrollment, study conduct and safety.

No formal interim analyses for futility or efficacy are planned. However, the aggregate rate of the primary outcome will be monitored throughout the study to assure a sufficient number of events. The following scenario may trigger an interim look for futility.

If we are not on target to reach the hypothesized number of events (in the blinded dataset) by the end of the follow-up period, we will assess whether an extension to follow-up is fiscally feasible. If follow-up is feasible, a non-binding futility analysis using an alpha-spending function will be conducted to determine whether it is worth extending follow-up.

Similarly, we will monitor the current trend of treatment in this patient population. The following scenario may trigger an interim look for efficacy if applicable.

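### New MS symptoms count as adverse events and also as primary-endpoint events; Section 6.5 does not separate them, so pooled AE and SAE totals are modestly diluted in favour of ocrelizumab if the drug works

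*Combined protocol and SAP*

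**What the plan says.** Section 2.3 makes safety a between-arm comparison: "The safety objectives for this study are to evaluate the safety of ocrelizumab compared with placebo".

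Section 5.2.1 defines an AE without regard to attribution and lists among its examples events not seen before, "including signs or symptoms associated with multiple sclerosis that were not present prior to the AE reporting period". The studied condition is exempted only in a later bullet: "Preexisting medical conditions (other than the condition being studied) judged by the investigator to have worsened". That bullet concerns worsening of something already present, so it does not reach a first MS symptom. Section 5.2.2 adds the seriousness filter: "An AE should be classified as an SAE if the following criteria are met".

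Section 6.4.1 gives the clinical part of the primary endpoint as a "neurological event resulting from CNS demyelination as evidenced by acute or progressive clinical syndrome consistent with MS", and Section 4.5.12 says that relapses confirmed by the adjudication committee count toward it.

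Section 6.5 covers all AEs, SAEs, AESIs, fatal AEs and AEs leading to treatment discontinuation; these "will be summarized by mapped term, appropriate thesaurus level, and severity grade". It mentions no split by endpoint status.

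On the collection period, Section 5.3.1 says that reporting "ends 24 weeks following the last administration of study treatment or study discontinuation/termination, whichever is earlier". Footnote u of the Schedule of Activities (Appendix 1) says instead that AEs are reported for the whole study.

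**The concern.** Patients enter with RIS and without MS symptoms, so nearly every first clinical MS event inside the AE window meets the AE definition. Section 4.5.12 sends neurologic events to their own eCRF but does not take them off the AE form, and the Physical Examinations section sends new clinically significant abnormalities to it. One relapse can therefore be counted as an efficacy failure and as a harm.

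The rule reads the same in both arms, but the counts it produces will not be equal if the trial's hypothesis is true. The better ocrelizumab prevents clinical events, the lower its AE, SAE and discontinuation counts, for a reason unrelated to tolerability. In people without symptoms the balance of benefit and risk is the central question, and a pooled safety total that contains part of the benefit blurs it.

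**Working it through.** The plan states no AE or SAE total, so there is no figure of its own to reproduce. Its statement on events and power is not used here; only the assumed event rates are.

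**Inputs**
- Clinical event in about one-third of RIS patients within 5 years (Background on Radiologically Isolated Syndrome), applied to placebo.
- 33% against 20% with the composite endpoint by 4 years, and 10% annual dropout (Determination of Sample Size).
- About 100 patients, 1:1, so 50 per arm.
- Background SAE risk 6.9% and any-AE risk 83.3%, the ocrelizumab figures in relapsing MS (Background on Ocrelizumab).
- Last dose at Week 48, plus 24 weeks, gives Week 72, or 1.38 years.
- Share of MS events that are serious, s: not in the documents; assumed 10%, 25% or 50%.

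**Hazards per year**
- Placebo: −ln(1 − 1/3)/5 = 0.0811.
- Hazard ratio: ln(0.80)/ln(0.67) = 0.557. This belongs to the composite; applying it to clinical events is an assumption.
- Ocrelizumab: 0.557 × 0.0811 = 0.0452.
- Dropout: −ln(0.9) = 0.105.

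**Patients with an MS-symptom AE**

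Cumulative incidence = h/(h + d) × (1 − exp(−(h + d)T)).
- T = 1.38 years: 9.87% placebo, 5.63% ocrelizumab; difference 4.24 points (4.9 against 2.8 of 50 patients).
- T = 4 years: 22.86% placebo, 13.58% ocrelizumab; difference 9.28 points (11.4 against 6.8 of 50).

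**Built-in placebo SAE excess**

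With independence, SAE risk = 1 − (1 − 0.069)(1 − s × incidence). The between-arm difference is therefore 0.931 × s × (difference in incidence).

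| Window | Clinical rate | s = 10% | s = 25% | s = 50% |
|---|---|---|---|---|
| To Week 72 | one-third by 5 years | 0.4 | 1.0 | 2.0 |
| To Week 72 | half that hazard | 0.2 | 0.5 | 1.0 |
| To 4 years | one-third by 5 years | 0.9 | 2.2 | 4.3 |
| To 4 years | half that hazard | 0.5 | 1.2 | 2.4 |

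Values are percentage points. In the first row they amount to 0.2, 0.5 and 1.0 patient of 50.

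**Any AE, if every MS event counts**

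(1 − 0.833) × 4.24 = 0.7 points to Week 72, and (1 − 0.833) × 9.28 = 1.6 points to 4 years.

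**What this does to a real excess of harm**

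Suppose non-MS SAE risks of 7% on placebo and 12% on ocrelizumab (assumed), a true excess of 5.0 points. Leaving dropout out, MS events occur in 10.6% and 6.1% to Week 72. The observed excess is then 4.5, 3.9 or 2.7 points for s = 10%, 25% or 50%. Over 4 years (27.7% and 16.5%) it is 3.9, 2.2 or −0.6 points.

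**The case against.** A reader might infer that every AE and SAE total is contaminated and that an excess of harm on ocrelizumab would be hidden. The documents do not support that:

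- **Not every total.** An MS symptom reaches the SAE count only if it meets a seriousness criterion, and hospitalization for scheduled therapy of the target disease is not reportable. AESIs are limited to Hy's law cases and suspected transmission of an infectious agent by the study drug, so they are untouched.
- **Not hidden.** Summaries are by mapped term, and the recording rule favours a diagnosis: "If known at the time of reporting, a diagnosis should be reported rather than individual signs and symptoms". A coded relapse stays visible, and an excess of infections sits in its own rows. Symptoms recorded before a diagnosis may still scatter over several terms, and term rows do not correct a pooled count.
- **Short window.** Under Section 5.3.1 routine collection ends near Week 72. After that only SAEs attributed to study treatment are reported, which placebo conversion would hardly satisfy.
- **Small against noise.** At 6.9% risk and 50 per arm, the standard error of an SAE difference is √(2 × 0.069 × 0.931/50) = 5.1 points, and no safety test is planned.
- **Inputs lean high.** One-third by 5 years implies 27.7% by 4 years, which is 27.7/33 = 84% of the planned composite rate and leaves little room for radiologic-only first events.
- **An opposing effect.** Sections 3.1 and 4.4.1 take patients out of the study after a confirmed relapse. That shortens AE collection in the arm with more relapses and lowers its counts.

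All of this stands as a limit on size. It does not remove the mechanism, which comes from a stated definition and not from a missing detail. Section 6 defers full analysis details to the SAP, so there is a natural place for the remedy.

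Two further points hold. The PML text in Section 5.1.1.2 warns that early PML can resemble a relapse, which argues against making a table without relapses the main one. And although a reader might infer that the iDMC would see an endpoint component by arm, its charter is not among the documents, so nothing can be said about its tables.

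**Conclusion.** The point holds in a limited form. First MS symptoms are AEs by definition, the confirmed ones are also endpoint events, and Section 6.5 does not separate them. If ocrelizumab reduces clinical events, pooled AE, SAE and discontinuation totals are diluted in its favour. To Week 72 the SAE effect is about 0.4 to 2.0 points, at most about one patient of 50, and about half that at half the clinical rate; the any-AE effect is 0.7 points. The range of 0.9 to 4.3 SAE points holds only with collection throughout the study. Substantial masking needs that long window with about half the events serious, or nearly all of them serious within the short one.

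These sizes rest on the background clinical rate, a composite hazard ratio applied to clinical events, independence, and an assumed serious share. Earlier exit after relapse offsets part of the effect by an amount the documents do not allow one to estimate. This is an inexpensive improvement to the safety analysis and does not invalidate the planned tables.

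**What to change.** Keep AE collection, safety reporting and the all-inclusive tables as they are. In Section 6.5 or the SAP, before unblinding:

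1. Pre-specify a parallel set of AE, SAE, severity and AE-leading-to-discontinuation totals that excludes adjudication-confirmed, protocol-defined neurologic events.
2. Tabulate those excluded events by arm.
3. Add exposure-adjusted rates, because confirmed relapse ends participation and follow-up may differ between arms.
4. Reconcile Section 5.3.1 with footnote u of Appendix 1, so that the period covered by the totals is unambiguous.

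The adjudication result is already collected, so the cost is a short text change and a second set of tables. No event is dropped from view, and fixing both versions in advance prevents a later choice of which total to headline.

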Complete physical examination ^h		x	x	x	x	x	x	x	x	x	x	x	x	x
EDSS		x	x		x	x	x	x	x	x	x	x	x	x
Neurologic examination ⁱ		x	x	x	x	x	x	x	x	x	x	x	x	x
Prescreen MRI	x ^w													
MRI brain ^{p,q}		x			x	x	x	x		x		x	x ^r	x ^r
MRI C-spine ^{p,q}		x			x	x	x	x		x		x	x ^r	x ^r
Symbol Digit Modality test for cognition	x*		x		x	x	x	x	x	x	x	x	x	x
Neuro QoL	x*		x		x	x	x	x	x	x	x	x	x	x
Assessment of neurologic event			x	x	x	x	x	x	x	x	x	x	x	x
Hematology, chemistry, and urinalysis ^j (Local lab)		x	x	x	x	x		x		x	x	x	x	x
Pregnancy test ^k		x	x	x	x	x								x
Hepatitis screening		x												
Hepatitis B virus DNA test ^l		x												

	Pre-screening (family members)	Screening ^a	Double-Blind Phase ^v											Unscheduled Visit ^b	Study Completion/ Early Termination ^c
Week	-6	-6	0 Baseline	2	24	48	72	104	130	156	182	208			
Visit Windows (days)	-45-1	-45-1	(-28)	(± 7)	(± 7)	(± 7)	(± 7)	(± 7)	(± 7)	(± 7)	(± 7)	(± 7)			
Quantitative Ig (total Ig, IgG, IgM, and IgA) (local lab)		x													
Quantitative Ig (total Ig, IgG, IgM, and IgA) (central lab)			x ^x		x	x	x	x	x	x	x	x	x	x	x
Lumbar puncture/CSF analysis (local lab and biomarkers) ^{m,p,s}			x ^x					x					x	x ^t	x ^r
Peripheral blood sample for biomarkers ^{m,s,t}	x		x ^x		x	x	x	x	x	x	x	x	x	x	x
Peripheral blood sample, paired with CSF			x ^y					x ^y				x ^y	x ^y	x ^y	
Serum samples for biomarkers ^{m,s}	x		x ^x		x	x	x	x	x	x	x	x	x	x	x
Gingival swab for storage	x [*]		x ^x		x	x	x	x	x	x	x	x	x	x	x
Adverse events ^u		x	x	x	x	x	x	x	x	x	x	x	x	x	x
Concomitant medications review		x	x	x	x	x	x	x	x	x	x	x	x	x	x
Randomization IxRS		x													
Methylprednisolone and antihistamine premedication ⁿ			x	x	x	x									
Ocrelizumab or placebo administration ^o			x	x	x	x									

eCRF = electronic Case Report Form; EDSS = Expanded Disability Status Scale; HBcAb = hepatitis B core antibody; HBsAg = hepatitis B surface antigen; HBV = hepatitis B virus; HepCAb = hepatitis C; MRI = magnetic resonance imaging; MS = multiple sclerosis; NfL = neurofilament light; WGS=Whole genome sequencing; PBMC=peripheral blood mononuclear cells; CSF= cerebrospinal fluid.

Note: (x) indicates that an assessment will only be done if needed.

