^q All MRIs will be read by a central reading center. Prior to initiation of study drug a QC report for the Screening MRI scan must have been received from the centralized reading center confirming scan passed QC. The brain MRI requires at least 2 business days from scan receipt to be quality checked before dosing of study drug. Screening MRIs must also be confirmed by the central MRI reader to meet 2017 McDonald criteria for dissemination in space prior to patient randomization. Contrast agent (gadolinium) required only at screening MRI and annually (Weeks 48, 104, 156, and 208).

^r To be obtained/Performed optionally, at the Investigators discretion, in case of neurologic event or suspected neurologic event suggestive of MS.

^s Biological samples may be sent to central laboratory, local laboratory or other academic laboratory and specialized sites for final processing, analysis and reporting due to cell viability and biomarker recovery, such as but not limited to B cell, T cell and innate immune cell subset samples in CSF. Please refer to laboratory manual for details.

^t A PD DNA sample will be collected for patient genotyping (whole genome sequencing; WGS) at the Baseline visit. If the DNA sample is not collected at the baseline visit, it may be collected at any subsequent visit. Collection and submission of this sample is contingent upon the review and approval of the exploratory research by each site's IRB/EC and, if applicable, an appropriate regulatory body. If a site has not been granted approval for WGS sampling, collection of this sample will not be applicable at that site.

^u Adverse events will be reported throughout the study.

^v The primary analysis for this study is event driven, therefore the study duration in the double-blind phase will vary for each patient. In the event that the requisite number of events have accumulated study-wide before the minimum 3-year follow-up, patients will then be unblinded and followed for a minimum of 3 years.

^w Pre-screening MRI scans must include FLAIR sequences to establish whether the individual meets 2017 McDonald criteria for DIS. Pre-screening MRIs will be interpreted by site PIs to determine whether they meet 2017 McDonald criteria for dissemination in space. Individuals established to have RIS in this way must subsequently undergo a full, screening MRI as noted elsewhere.

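### Section 5.3.1 limits adverse-event, SAE and death reporting to first dose through 24 weeks after the last dose, while Section 5.3 and the Schedule of Activities cover the whole study

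*Combined protocol and SAP*

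**What the plan says.** Two reporting rules stand side by side in the combined protocol and SAP.

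**The limited period.** Section 5.3.1 gives the start: "Reporting period begins after informed consent is obtained and initiation of study treatment". It says the period "ends 24 weeks following the last administration of study treatment or study discontinuation/termination, whichever is earlier", and adds: "After this period, investigators should only report SAEs that are attributed to prior study treatment". Section 5.4.2 (Deaths) refers back to Section 5.3.1 and covers "All deaths that occur during the protocol-specified AE reporting period", whatever their cause.

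**The whole study.** The opening of Section 5.3 makes the investigator responsible for ensuring that "all AEs and SAEs that are observed or reported during the study, are collected" and reported. In Appendix 1, the row labelled "Adverse events ^u" is marked at screening, at all ten visits from baseline to Week 208, and at the unscheduled and completion/early-termination visits. Its footnote reads: "Adverse events will be reported throughout the study".

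The definitions divide in the same way. Section 5.2.1 counts a worsened pre-existing condition if the change falls within the reporting period. Section 5.4.2 says "A preexisting medical condition should be re-assessed throughout the trial and reported as an AE or SAE only if" it worsens during the study. Section 5.2.1 also admits, where applicable, events before treatment assignment that arise from protocol-mandated interventions. Section 5.3.1 starts later than that.

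**The concern.** The safety objectives (Section 2.3) compare the nature, frequency, severity and timing of AEs between ocrelizumab and placebo, and they name AEs of biomarker sample collection as an endpoint. A site that follows Section 5.3.1 literally has no duty under it to report late non-serious AEs, late SAEs judged unrelated, or late deaths judged unrelated. A site that follows the schedule reports all of them. The Section 6.5 tables begin at the first dose and have no stated end, so they would mix the two practices. Late SAEs would also enter only through individual attribution, which is a weaker basis for comparing arms than complete ascertainment.

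The sample-collection endpoint is exposed at both ends. The baseline lumbar puncture is required before randomization for patients who have never had one (Section 4.2.1) and may precede dosing by up to 4 weeks (Appendix 1, footnote p). The optional punctures at Weeks 104 and 208 come after the period has closed.

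The protocol's own pharmacology also outlasts the period. Section 5.1.1 reports a median of 72 weeks to B-cell repletion after the last infusion (range 27 to 175 weeks).

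**Working it through.** The plan gives no figure to reproduce. The check compares the texts above and then applies calendar arithmetic to the schedule.

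**Inputs**
- Period end = last dose + 24 weeks (Section 5.3.1).
- Dosing visits: Weeks 0, 2, 24 and 48 (Section 3.1).
- Visits from baseline: Weeks 0, 2, 24, 48, 72, 104, 130, 156, 182 and 208, ten in all, with a ±7-day window after baseline (Appendix 1).
- Screening: up to 45 days before baseline (Appendix 1, footnote a).
- Dropout: 10% per year (Section 6.1).

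**Share of the 208 scheduled weeks after the period closes**

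| Last dose | Period ends | Weeks after | Share | Visits after |
|---|---|---|---|---|
| Week 48 | 48 + 24 = 72 | 208 − 72 = 136 | 136/208 = 65.4% | 104, 130, 156, 182, 208 (5 of 10) |
| Week 24 | 24 + 24 = 48 | 208 − 48 = 160 | 160/208 = 76.9% | the above plus 72 (6 of 10) |
| Week 2 | 2 + 24 = 26 | 208 − 26 = 182 | 182/208 = 87.5% | the above plus 48 (7 of 10) |

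Moving the Week 48 dose by ±7 days puts the end at Week 71 to 73, which leaves 137 weeks (65.9%) to 135 weeks (64.9%). With an end at Week 71, a Week 72 visit held on schedule also falls outside, making 6 of 10.

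**Allowing for dropout.** Assume exponential dropout with hazard −ln(0.9) = 0.1054 per year and a last dose at Week 48 for everyone.
- Person-time over 4 years, per patient: (1 − 0.9^4)/0.1054 = 3.264 years.
- Person-time after Week 72 (72/52 = 1.385 years): (0.9^1.385 − 0.9^4)/0.1054 = 1.976 years.
- Share after the period: 1.976/3.264 = 60.5%, or about 198 of 326 patient-years per 100 patients.

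**Before the period.** Up to 45 days of screening precede it, as do the 28 days in which the baseline puncture may be done. The screening mark in the AE row therefore lies outside Section 5.3.1.

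**B-cell repletion.** After a Week 48 dose, the protocol's figures place it at Week 48 + 72 = 120, with a range of 48 + 27 = 75 to 48 + 175 = 223. The whole range lies after Week 72.

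**The case against.** The strongest reply is that Section 5.3.1 is an onward-reporting window and that the schedule governs collection. Section 5.3.1 refers to patients exposed to the supplier's product, and the section on exchanging single case reports with the supplier uses similar language. Section 4.5 requires every scheduled activity to be performed and documented, and AE review is scheduled to Week 208. Section 3.1 has safety evaluated throughout the study.

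Much late information would also be captured elsewhere. Clinically significant examination and MRI findings go to the AE eCRF, and PML must be reported as an SAE. Section 5.2 includes all deaths among the safety assessments. Section 6.5 summarises deaths without an end date. Attributed SAEs remain reportable after the study. Section 5.2.1 counts complications of protocol-mandated procedures as AEs without a time limit.

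This limits the loss but does not remove the contradiction. The documents never separate collection from reporting: Section 5.3 joins the two, and footnote u itself speaks of reporting. The procedure-complication item defines what an AE is, not when it is reported. None of these passages displaces the explicit restriction in Section 5.3.1 or the cross-reference that ties deaths to it.

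It is also fair that the calendar shares ignore dropout, discontinuation after a confirmed relapse, and dosing delayed beyond the visit window. Dropout alone lowers the share from 65.4% to 60.5%, which does not change the conclusion. Pre-dose puncture events cannot inform the treatment comparison, but they do belong to the named sample-collection endpoint.

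**Conclusion.** The contradiction is real, and it affects both the start and the end of AE reporting. For a fully dosed patient followed to Week 208, 65% of the scheduled weeks fall after the Section 5.3.1 period, or about 60% of person-time at the planned dropout rate. The share is larger for patients who stop dosing early. All scheduled lumbar punctures can fall outside the period. The figures assume that the period ends exactly 24 weeks after the last dose and that follow-up runs to Week 208. They measure exposure to the gap; they do not estimate how many events would be missed, and capture through other passages makes the loss partial. The point should be corrected because it bears directly on the placebo comparison of safety and on a named safety endpoint, and because AEs not recorded at the time may be hard to recover reliably.

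**What to change.** - Amend Section 5.3.1 and the deaths paragraph of Section 5.4.2 to agree with Section 5.3, footnote u and the AE row. AEs, SAEs and deaths should be recorded in both arms, regardless of attribution, from screening to study exit, including any extension of the double-blind phase under Section 3.1.
- If a 24-week limit is needed, state that it applies only to transmission to the drug supplier.
- Use the same period for pre-existing conditions in Sections 5.2.1 and 5.4.2.
- State the period in Section 6.5. List pre-dose procedure AEs separately there, since those tables start at the first dose.

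The cost is protocol wording, additional eCRF entries at visits that already include AE review, and possibly alignment with the supplier's pharmacovigilance agreement.
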